4.2. INCLUSION / EXCLUSION CRITERIA

Inclusion Criteria: In order to be eligible to participate in this study, an individual must meet all of the following criteria:

1. Provision of signed and dated informed consent form from patient or legal authorized representative (LAR)
2. Subject or LAR stated willingness to comply with all study procedures and availability for the duration of the study
3. Males and female (of unlikely childbearing capacity) aged over 18 years
4. Exhibiting signs and physical examination findings suggestive of an acute ischemic infarction (with either):
 - a. A target mismatch profile of CT-perfusion or MRI determined by RAPID automated software to have a ratio of PWI_{T_{max}>6} lesion volume/DWI lesion volume >1.2 and NIHSS $\geq 1^{54}$
 - b. A RAPID automated software calculated non-contrast CT-head ASPECT score of 10 and LKW ≤ 12 hours (in patients with symptoms discovered upon waking, the LKW is defined at the midpoint between going to sleep and awakening based on previous studies that suggest most strokes during sleep occur close to awakening)⁵⁵
5. Normoxic; a pulse oximetry of 94% or greater at time of screening without the use of supplemental oxygen

Exclusion Criteria: An individual who meets any of the following criteria will be excluded from participation in this study:

1. Current use of supplemental oxygen
2. Prisoner
3. Pregnancy or those of likely childbearing potential (i.e. age <50, no documented negative pregnancy in last 24 hours, no documented history of hysterectomy)
4. Documented blood glucose <70mg/dL
5. Concurrent treatment with another investigational drug or other intervention
6. Documented history of any of the following chronic respiratory illness that require pulmonary vasodilators or supplemental oxygen at baseline: Chronic Obstructive Pulmonary Disorder (COPD), Emphysema, Interstitial Lung Disease, Restrictive Lung Disease, Pulmonary Hypertension, Pulmonary Fibrosis
7. Documented history of any of the following autoimmune diseases: systemic lupus erythematosus, rheumatoid arthritis, scleroderma, primary biliary cholangitis, multiple sclerosis, inflammatory bowel disease

8. Currently being treated for an acute myocardial infarction and/or decompensated heart failure at the onset of initial ED presentation as reported by the ED provider
9. Plans for treatment with either IV tPA (alteplase) or endovascular therapy

4.3. STUDY INTERVENTIONS

Enrolled subjects will be randomized to receive either brief hyperoxia treatment (defined as 15L/min supplemental oxygen) or medical air (at 15L/min) via a partial non-rebreather mask for four hours from the time of study initiation (T_1). Supplemental oxygen is routinely used to correct and/or prevent hypoxemia (low blood oxygen content, defined as an arterial oxygen content of less than 60-75mmHg). To avoid invasive monitoring of arterial oxygen content, pulse oximetry is routinely used to monitor for hypoxia with values less than 90-94% considered low in most clinical scenarios. Unfortunately, there are limitations with pulse oximetry and based on the oxyhemoglobin dissociation curve and a SpO_2 of 97% could represent any PaO_2 above ~90mmHg. Thus, pulse oximetry alone is not an ideal mechanism to determine hyperoxia. Based on mouse models, this study targets a PaO_2 of 200-400mmHg in the hyperoxia treatment group. In a previous study of cardiac catheterization patients, delivery of 10-15L/Min facemask oxygen resulted in average PaO_2 in the 400s.

In this study, oxygen is being used as a drug. However, an IND exemption is requested. We feel that the use of oxygen in this scenario to prevent hypoxemia in the ischemic tissue by creating a global hyperoxia environment meets the criteria for an IND exemption. Specifically, this protocol will: be conducted in compliance with requirements for IRB review and the requirements concerning the promotion and sale of drugs; not be in support of a new indication for use or change in labeling or advertising of oxygen; not invoke exemption from informed consent; not involve a route of oxygen administration or dosage level that significantly increase the risks of the drug product. Additionally, there is no consistent predetermined dosage of oxygen that can be universally applied to all clinical contexts to determine who needs supplemental oxygen and at what dose. This decision is left to the clinical judgement of the practicing medical provider. For example, in patients undergoing procedural sedation in the ED, supplemental oxygen may be provided despite having a pulse oximetry reading greater than 92-94% to prevent desaturation. According to the AHA guidelines for stroke patients, hypoxia that they suggest warrants supplemental oxygen use is defined as a pulse oximetry of less than 94%, but the data behind this exact recommendation is also very weak⁵⁰.

Supplemental oxygen wall connections and/or oxygen tanks are standard in every hospital room and ambulance. Additional oxygen tanks are available for patients during transport as needed. Oxygen will be administered using standard oxygen tubing and a partial non-rebreather facemask. It is approved for the treatment and preventions of hypoxia and hypoxemia. Hypoxia is often measured non-invasively by a pulse oximetry and thresholds to begin supplemental oxygen therapy vary based on disease entity and provider discretion. Medical oxygen can be supplied in numerous methods, but for the purpose this study it will be supplied at flow rates of 15L/min via a non-rebreather facemask. This generally is considered to provide a fraction of inspired oxygen (FiO_2) of 0.45-0.9 in most patients and should result in systemic hyperoxia with a PaO_2 >200mmHg⁵⁶.

5. RECRUITMENT METHODS

The target sample population will include adults over the age of 18 years with an acute ischemic stroke. The demographics of the sample will reflect that of Denver and Arapahoe Counties, the major geographical recruitment area – approximately 49.8% and 50.4% female, 54.5% and 59.9% White, 29.7% and 19.5% Hispanic, respectively. There will be no specific recruitment strategies for specific demographic populations. However, given that older age is associated with increased stroke incidence, it is estimated that most subjects will be elderly.

All suspected stroke patients undergoing a rapid stroke evaluation with a CT-perfusion or non-contrast CT-Head with RAPID ASPECT score and evaluation by the stroke team at the University of Colorado Hospital will be considered for enrollment. Patients will be screened upon arrival to the ED by a trained Emergency Department Research Assistant or other study personnel using a standard recruitment script. Consent, enrollment, and initiation of treatment will be performed by a study personnel. At UCH-Memorial, only the study research assistants who are trained in the how to conduct clinical research, including the more rigorous consent process associated with research compared to routine clinical care will screen, consent, and enroll subjects. The site-PI and site-sub-I will be available for clinical questions. These research team members will undergo yearly training provided by the study PI to ensure familiarity with the consent process and study activities. Additionally, the study PI will review consent documents, screening logs, and subject assessments on a monthly basis to ensure compliance and she will be available in real time, by video chat or phone for any questions.

During the treatment, the study team will stress the importance of the 3-month follow-up phone interview and two potential phone contacts will be gathered if possible. The remainder of the study activities will occur while the patient remains in the ED or hospitalized. No specific recruitment strategies will be employed for historically underrepresented minorities.

This study will not include vulnerable populations with the exception of potentially cognitively impaired subjects due the possibility of altered mental status secondary to the ischemic injury from their stroke and elderly patients with cognitive impairment from age-associated diseases such as dementia. However, in order to protect these subjects, they will only be included when a LAR is available for consent. Given the short duration of intervention while patients remain hospitalized or in the ED and follow up limited to 3 months, we anticipated only a few subjects deemed to have capacity at enrollment will become classified as vulnerable populations (i.e. develop cognitive impairment or become incarcerated) during the study. However, all subjects will be reevaluated at 4 hours by study personnel for possible changes in their capacity to consent.

Given that subjects will be committing to a follow-up phone interview, subjects will be provided a \$25 gift card for their participation at the T₃ time point.

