In order to minimize bias, efforts will be made to blind the observers to the control versus treatment group. However, medical air and oxygen have different ED wall supply connectors that could be potentially identified by both the patient and the study personnel. Thus, full blinding cannot be guaranteed. To minimize bias, ED staff will initiate a given intervention and they will be instructed to not tell the patient which was started on the patient. To avoid bias with regards to infarct lesion size,

the automated RAPID software will be used to perform lesion measurements and screening for enrollment based on target mismatch. The CT-Perfusion and automated CT-ASPECT (Alberta Stroke Program Early Computed Tomography Score) have been previously used to identify patients who are early in their acute stroke trajectory with a small core infarct volume and remaining area suggestive of salvageable tissue⁵². Both are standardized quantitative or semi-quantitative measurements that can be automatically computed by RAPID software, thereby eliminating the subject assessments of providers to identify patients with potentially salvageable penumbral tissue. The assessment of the NIHSS will be extracted from the initial stroke team consult note and subsequent assessments will be video-recorded by study personnel. Videos of the assessment will be stored using a unique file name and stored in the secure School of Medicine Server. They will be reviewed in groups in a blinded fashion for scoring. At the conclusion of the study and required time for maintaining study data, all videos will be destroyed. In the case where videotaping is not permitted by a performance site, NIHSS-trained personnel (RN, MD, or PA) who are caring for the patient, will be asked to complete and score the NIHSS. In the event that the clinical team is unable to complete this assessment, the research team, also NIHSS-trained, will complete this assessment. In all cases, who/how the NIHSS was completed will be documented and blinding to the study intervention will be attempted when possible.

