- a. NIHSS score: The NIH Stroke Scale (NIHSS) is a standardized tool to measure stroke severity. Study observers will be required to complete the National Stroke Association NIHSS certification online course. As part of the training, interrater reliability between study observers will be determined. This assessment is part of all initial stroke evaluations by ED and/or neurology physicians. Subsequent NIHSS assessments at T₁ and T₂ will be video-recorded by trained study personnel and/or EDRA. However, in the case the videotaping is not permitted by a performance site, NIHSS-trained personnel (RN, MD, or PA) who are caring for the patient, will be asked to complete and score the NIHSS. In the event that the clinical team is unable to complete this assessment, the research team, also NIHSS-trained, will complete this assessment. In all cases, who/how the NIHSS was completed will be documented and blinding to the study intervention will be attempted when possible. The preference will be to have the score determined in a blinded manner upon review of the assessments at a subsequent time point.
- b. mRS scoring: The modified Rankin Scale, mRS, is another functional scale that assesses for neurologic disability on a scale of 0-6 (0-asymptomatic; 6-death). A historical mRS will be extracted from the patient chart and/or calculated at patient presentation. Patients and/or their caregivers will be interviewed by phone at 3months using a series of standardized questions regarding their neurologic disability to determine this score.

4. *Arterial puncture and ABG* – Hyperoxia (PaO₂ >200mmHg) will be confirmed by an ABG sample from subjects. These will be obtained by licensed medical personnel trained to perform arterial punctures (i.e. nurses, physicians, respiratory therapists). Standard procedures for obtaining an arterial blood sample will be employed to reduce the risk of complications. To decrease variability between ABG analysis, ABGs will be performed using standard operating procedures. The site of the arterial puncture and correlating extremity will be evaluated for potential complications (increased pain, discoloration, erythema, hematoma formation, bleeding). If there are any concerning findings on these exams, the study PI will be notified and the subject will be monitored again at T₂ and/or until the event is felt to resolve.

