16. DATA AND SAFETY MONITORING PLAN

Only trained research assistants at UCH-Memorial will be responsible for consent of subjects, with support of the site-PI, site-sub-I and/or PI as needed (see consent section for details). The research assistants at UCH-Memorial will be responsible for completion of patient assessments and reporting of potential safety issues and/or protocol violations to the site-PI, site-sub-I and PI. In addition, the PI will review data assessments uploaded to REDCap monthly for completion. Site screening/enrollment logs will be reviewed monthly. Study personnel at both sites will undergo an initial training by the PI at onset of study which will include review of the study protocol, inclusion/exclusion criteria, the consent process, methods of sample collection and processing, patient assessments, and standardized chart review methods. The trained research assistants at both sites will have complete required human subjects research trainings and specific training to ensure accuracy of the NIHSS scoring prior to completing these assessments on any subjects. A standard operating procedures (SOP) manual will also be provided for references. Training will be refreshed annually or sooner if there are protocol changes and/or any compliance concerns.

Safety oversight will be under the direction of a Safety Monitoring Committee (SMC), composed of individuals with the appropriate expertise, including stroke, neurocritical care, and emergency medicine. Members of the SMC will include members of the investigative team. However, measures will be in place to minimize perceived conflict of interest. The SMC will meet at least semiannually to assess safety and efficacy data on each arm of the study.

Assessment of safety measures and adverse events:

Study personnel and the subject's treating physician will regularly monitor subjects for safety measures and adverse events. This includes practices that are associated with routine patient care (i.e. vital sign assessments, assessment of neurologic deterioration, development of respiratory compromise). Specific monitoring includes the following:

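### Section 5 has study personnel start the gas, while Section 4 gives that task to ED staff to limit bias; following Section 5 reveals the arm to a member of the team that assesses NIHSS

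*Combined protocol and SAP*

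**What the plan says.** Section 4 (Study Design) explains why the treatment can be recognised at the bedside: the two gases use "different ED wall supply connectors that could be potentially identified by both the patient and the study personnel". It concedes the limit, "Thus, full blinding cannot be guaranteed", and then gives a countermeasure: "To minimize bias, ED staff will initiate a given intervention and they will be instructed to not tell the patient".

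Section 5 (Recruitment Methods) assigns the same task to others: "Consent, enrollment, and initiation of treatment will be performed by a study personnel".

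On who assesses, Section 7 (item 3a) says that the NIHSS at T1 and T2, which Table 1 places at 4 and 24 hours, "will be video-recorded by trained study personnel and/or EDRA". The preferred score comes from later blinded review. Where a site does not allow filming, NIHSS-trained clinical staff looking after the patient are asked to score. The last resort is the research team: "In the event that the clinical team is unable to complete this assessment, the research team, also NIHSS-trained, will complete this assessment". Section 16 adds: "The research assistants at UCH-Memorial will be responsible for completion of patient assessments". It also has the research assistants at both sites trained in NIHSS scoring before they assess any subject.

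**The concern.** Starting the gas means handling the connector, so whoever does it knows the arm. Section 4 places that knowledge with ED staff for a stated reason. Section 5 places it with the study team, whose members then carry out NIHSS assessments. A site could follow Section 5 to the letter and defeat a safeguard that Section 4 describes.

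At stake is the change in NIHSS over the first 24 hours, a secondary outcome meant to inform later trials. NIHSS items need judgement, both in how the examination is conducted and in how it is scored. An examiner or scorer who knows the arm and expects benefit could move the comparison in that direction.

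**Working it through.** The point depends on no sample size, effect size or error rate, so there is no figure to reproduce. The check is a comparison of the relevant text.

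1. **Who starts the gas.** Section 4: ED staff, as a measure against bias. Section 5: study personnel, in the same sentence as consent and enrollment. Both are current text.

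2. **Whether the two terms could mean the same people.** Section 4 names ED staff and study personnel separately within one paragraph. Section 6 describes the research personnel who approach subjects as the PI or a research assistant. The terms are distinct, so the sections conflict.

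3. **Whether any section resolves it.** None does. For UCH-Memorial, Section 5 lists screening, consent and enrollment as the research assistants' tasks and does not repeat initiation. The conflict at that site therefore rests on the general sentence just before.

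4. **What starting the gas reveals.** By Section 4's own account, study personnel could recognise the connector. The person who attaches the line certainly can.

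5. **Where that knowledge could reach the NIHSS.** There are three scoring routes, in order:
   - *Later blinded scoring from video.* The scorer is protected, but the filmed examination may be conducted by someone who knows the arm. Nothing keeps the connector out of the picture.
   - *Clinical staff caring for the patient,* if filming is not permitted. Blinding is best effort.
   - *The research team, live,* if filming is not permitted and clinical staff cannot score. Blinding is again best effort. This is where Section 5 does most harm.

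6. **Whether starter and assessor must differ.** No section requires it. No section says that they are the same individual either. What is shown is exposure of the team.

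7. **Which time point the starter matters for.** Section 4.3 limits the gas to four hours. At the 24-hour NIHSS the connector should no longer be in use, so the arm is known mainly to those who connected or saw the gas earlier. Separating starter from assessor is therefore most useful at 24 hours. At 4 hours other routes remain, because Section 7 has adherence observed directly at the assessment time points.

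8. **Primary endpoint.** Section 17 measures time from ED arrival to randomization and start of intervention. Knowledge of the arm by a later assessor has little bearing on it.

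**The case against.** The strongest reply is that the protocol has several other protections, none of which Section 5 touches: later blinded scoring from video, automated RAPID lesion measurement, a medical-air control at the same 15 L/min flow through the same type of mask, and blinded biomarker assays. A reader might infer that ED-staff initiation is the only blinding step. The documents do not support that; it is the only step that governs who starts the gas. This part of the reply stands, and it bounds the risk.

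Second, live scoring by the research team is the last of three routes and needs two conditions to fail. That also stands. It does not cover the filmed examination, which an unblinded person may still conduct.

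Third, the protocol already admits that blinding is incomplete. That admission is the reason Section 4 gives for using ED staff, so it does not excuse another section that cancels the step.

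Fourth, restoring Section 4 is not a full remedy. Its instruction to ED staff is only to keep the arm from the patient, and clinical staff are the first fallback scorers, so knowledge of the arm would move to another group of possible scorers. This stands and shapes the fix: the rule has to attach to the individual who connects the gas, whichever group that person belongs to. A wider bar on anyone who merely sees the gas source would be impractical, given that study personnel observe adherence directly.

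**Conclusion.** The contradiction is real and should be corrected. Section 5 as written defeats a bias safeguard stated in Section 4 and exposes the 4-hour and 24-hour NIHSS to examiners, and in the last fallback to scorers, who may know the arm. The issue is moderate: it concerns a secondary outcome, the preferred scoring route is blinded, and the primary feasibility endpoint is little affected.

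The size of any bias cannot be estimated from the documents. Several stronger conclusions may be tempting but are not supported:

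- *That all 200 planned subjects are affected.* The documents do not say how many would be scored without video, or how often starter and assessor would coincide.
- *That a shift of, say, one NIHSS point would follow.* No figure for rating bias is given. The two-point difference in Section 17 is a stated detectable difference, in a study that the same section describes as not powered for secondary outcomes.
- *That adverse-event and mRS ratings are shown to be biased.* Section 16 reserves judgement of relationship to those qualified to diagnose, and expectedness to the PI. Section 7 does not name the 3-month interviewer, and Section 17 treats mRS as exploratory. No assessor blinding is described for that call, so a precaution is reasonable, but bias is not demonstrated.

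The verdict assumes that ED staff and study personnel are different groups, as Sections 4 and 6 indicate, and that a site may follow either section.

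**What to change.** 1. Amend Section 5 so that study personnel carry out consent and enrollment and ED staff start the gas, in line with Section 4.
2. Add to Sections 4 and 7 that the individual who connects the gas does not conduct or score that subject's follow-up NIHSS, including as a clinical-staff fallback scorer, and does not make the 3-month mRS call.
3. State that the gas connector is kept out of the NIHSS video frame.

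The protocol already records who completed each NIHSS and how, so the second rule can be checked from that record once the person who connected the gas is noted too.

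The cost is a few sentences and some task assignment among existing staff. Sample size, endpoints and treatment do not change. The fix does not make the trial fully blinded, and the protocol's statement to that effect should stay.
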